**Phase II (expansion cohort)**

The treatment dose for Phase II will be the MTD or the highest tolerable dose. At this dose level, additional 42 patients will be treated in order to provide information on the CR-rate of the combination.

Patients who achieve a CR/CRp (ANC  $\geq 1 \times 10^9/L$ ) may receive venetoclax maintenance treatment for up to one year. Dose reduction rules will be defined in case toxicities occur. Patients eligible for allogeneic stem cell transplantation with a suitable donor can proceed to transplantation and will be excluded from further study treatment.

	
Maintenance Therapy:
 
Patients eligible for maintenance treatment will receive 400 mg venetoclax QD per os as continuous treatment starting within 14 days after the remission assessment of the previous treatment phase for up to twelve 28-day cycles.

Treatment Flow Phase I and II
	

Sample Size
	
Depending on the number of DLT at lower dose levels up to a maximum of 18 patients may be enrolled in the phase I part;
 
For the phase-II part, in total 42 patients have to be treated at the MTD or the highest tolerable dose.

Safety
	
The decision to escalate to the next dose level will be taken by telephone conferences (safety calls) with participation of the investigators, pharmacovigilance and the sponsor (steering committee) on a regular basis after the DLT evaluation period of each dose level cohort. Continuous SAE monitoring will be performed in order to detect excess toxicities. In phase II, published reference values on the incidence of early mortality and toxicities <math>\geq</math> grade 3 from historical cohorts will serve as external control and landmarks; excess incidences <math>>10\%</math> will trigger extra consultation of the steering committee.

Cooperative Group
	
Study Alliance Leukemia (SAL)
 
For the phase-I part of the trial, 3 sites with experienced Early Clinical Trial Units will be selected for patient recruitment in order to ensure patient safety. For the

	expansion part, additional 7 sites will be added for recruitment with an estimated overall recruitment rate of 6 patients / month.

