Statistical Considerations	
The phase I part will be conducted according to the enhanced algorithms of a 3+3H design (Ji et al. J Clin Oncol 2013).
 
The phase II part will be performed as single stage study adopting the A'Hern design (A'Hern Stat Med 2001). The phase II part of the trial will test the null hypothesis that the CR/CRi rate is <math>\leq 45\%</math>. This benchmark for the CR/CRi rate was selected based on literature review of trials for this patient population. The primary efficacy analysis the CR/CRi rate will be calculated by the number of observed CR's/CRi divided by the total number of patients in the phase II full analysis set. We expect a CR/CRi rate of 65% with the combination treatment. This expectation is based on CR/CRi rates reported for the combination of venetoclax and demethylating agents in patients with de novo AML being around 70% (DiNardo ASH 2015, Pollyea ASCO 2016). The null hypothesis will be tested with the one-sample exact binomial test with a one-sided type one error probability of 5% and a power of 80%. Given 25 CR/CRis observed among the 42 patients treated at the MTD the null hypothesis will be rejected.

Anticipated Duration	
Entire Trial
 
First patient in to last patient out (months): 48 months
 
Recruitment period (months): 24 months
 
Follow-up period: 24 months after enrolment of last patient
 
Follow-up period per patient: minimum 24 months after study enrolment
 
AE reporting period: day 1 of V-MAC until 28 days after end of venetoclax treatment

Ancillary Research	
Biomarkers for response to venetoclax have not yet been established for patients with AML. Response may depend on the activation of specific intracellular signaling pathways. Identification of biomarkers might help to better interpret results from clinical trials, improve the design of future trials and to identify patient groups who benefit most from this drug. Moreover, venetoclax maintenance therapy may impact on pre-malignant clonal hematopoiesis especially when the founding clones are defined by mutations in chromatin modifiers (Shlush et al., Nature 2014 and Jeziskova et al., Int J Hematol 2015).

Therefore, we will set out to study changes in the clonal composition of hematopoiesis in patients who achieved a remission.

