## **8.2 Phase II – Expansion part**

### **8.2.1 Sample size**

In combination with low-dose cytarabine, the bcl2 inhibitor venetoclax has shown promising clinical activity with a CR+CRi rate of 54% in a frail elderly patient population receiving initial treatment for newly diagnosed AML(Wei et al., J Clin Oncol 2019). In addition, cytarabine may synergize with venetoclax by down-regulating Mcl-1. In a paper from 2011, Touzeau et al. showed synergy between ABT-737 and Ara-C in mantle cell lymphoma cell lines (Touzeau et al., Clin Cancer Res 2011).

We hypothesize that the combination of intermediate-dose cytarabine salvage plus venetoclax will have an increased antileukemic efficacy compared to standard salvage alone and that efficacy signals can already be shown in a small patient number in a phase-I/II expansion cohort. Historical data show: While only around 20% of frail patients who have been treated with low –dose cytarabine alone reach CRs, the combination with venetoclax results in an increase by 30% (Burnett 2007). Standard intensive relapse treatments produce CR rates of around 40-55% (Steinmetz et al., Ann Hematol 1999; Karanes et al., Leuk Res 1999; Pastore et al., Ann Hematol 2003; Larsson et al., Leukemia & Lymphoma 2012; Fiegl et al., Leukemia 2014; Ahmed et al., Leuk Res 2015; Thiel et al., Ann Oncol 2015; Bergua et al., Br J Haematol 2016). Assuming a similar beneficial effect of venetoclax in this setting, we assume a CR rate of 65% for the combination treatment of intermediate-dose cytarabine, mitoxantrone and venetoclax.

The phase II part will be performed as single stage study according to A'Hern (A'Hern Stat Med 2001). It will test the null hypothesis that the CR/CRi rate is  $\leq 45\%$ . This benchmark for the CR/CRi rate was selected based on literature review of trials for this patient population. We expect a CR/CRi rate of 65% with the combination treatment as the minimum required level of efficacy. This expectation is based on CR/CRi rates reported for the combination of venetoclax and demethylating agents in patients with de novo AML being around 70% (DiNardo ASH 2015, Pollyea ASCO 2016). To be able to reject the null hypothesis ( $H_0: p \leq 0.45$ ) in favor of the alternative hypothesis ( $H_1: p \geq 0.65$ ) at a one-sided significance level of 5% with 80% power 42 patients must be enrolled.

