### **8.2.2 Analysis sets**

#### **8.2.2.1 Full analysis set (FAS)**

The FAS consists of all patients with exposure to venetoclax and cytarabine with the MTD (including patients who received MTD in phase I part, even if they were excluded from the MTD analysis set).

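### The stated success rule (25 of 42) does not fit the set on which the primary test is run, because the full analysis set also takes in phase I patients treated at the MTD

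*Protocol*

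**What the plan says.** The Protocol describes an exact single-stage design in section 8.2.1: "The phase II part will be performed as single stage study according to A'Hern". The null CR/CRi rate is 45%, the alternative is 65%, and "at a one-sided significance level of 5% with 80% power 42 patients must be enrolled". The synopsis (Statistical Considerations) turns this into a count: "Given 25 CR/CRis observed among the 42 patients treated at the MTD the null hypothesis will be rejected".

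The primary endpoint is divided by the number of patients in the phase II FAS (synopsis, Statistical Considerations), and section 8.2.5 places all efficacy analyses in the FAS. Section 8.2.2.1 bases the FAS on having received both venetoclax and cytarabine at the MTD level, and a bracket then widens it: "including patients who received MTD in phase I part, even if they were excluded from the MTD analysis set". Section 8.2.5.1 prescribes an exact binomial test at a one-sided 5% level and gives no cut-off.

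On numbers, the synopsis says of the expansion: "At this dose level, additional 42 patients will be treated in order to provide information on the CR-rate of the combination". Section 3.3 repeats this, and section 3.1 speaks of enrolling 42 patients in the expansion part. The synopsis Sample Size row says, for the phase II part, that "in total 42 patients have to be treated at the MTD or the highest tolerable dose".

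**The concern.** The rule and the tested set have different sizes. Where 42 patients are enrolled on top of phase I, the FAS cannot be 42 unless expansion patients drop out of it. The only success count in the document therefore belongs to a number of patients that the primary analysis will probably not have. This is the trial's one confirmatory test, in an open-label study, and someone could later choose between 25 and a recomputed count once responses are known.

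Two further points concern who is added.

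- **Population.** Primary refractory patients may enter only the expansion part (sections 1.4 and 4.1). Section 1.4 also limits the escalation part to relapse more than 90 days after cytarabine, on the ground that such disease is again considered sensitive to the drug.
- **Timing.** Remission is assessed on days 28 to 45 (section 3.4). The decision to open the expansion considers all study data available from the escalation part (section 3.1), so phase I responses can be known when it is taken.

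**Working it through.** **Inputs.** Null rate p0 = 0.45, alternative p1 = 0.65, one-sided level 0.05, power 0.80, N = 42 (section 8.2.1). Cut-off r = 25 (synopsis, Statistical Considerations). Phase I patients at the chosen level: 3 or 6, inferred from the 3+3 rule in section 3.2. Patients replaced under section 4.4.2 come on top, since the FAS keeps those excluded from the MTD analysis set.

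**Formula.** For X distributed Bin(N, p): alpha = P(X ≥ r | p0) and power = P(X ≥ r | p1). The cut-off is the smallest r with alpha ≤ 0.05.

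**Step 1: the plan's own figure.** At N = 42, r = 24 gives alpha 0.0772, which is too high. r = 25 gives alpha 0.0415 and power 0.818. The smallest N meeting both targets is 42. The 25/42 rule is therefore correct for 42 patients.

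**Step 2: the FAS as defined.** 42 + 3 = 45 and 42 + 6 = 48, before any replaced patients.

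| N | Cut-off from the exact test | Alpha | Power | Alpha if 25 is kept |
|---|---|---|---|---|
| 42 | 25 | 0.0415 | 0.818 | 0.0415 |
| 45 | 27 | 0.0308 | 0.806 | 0.1017 |
| 48 | 28 | 0.0438 | 0.868 | 0.1998 |

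One count fewer is not enough: 26/45 gives alpha 0.0582 and 27/48 gives 0.0779.

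**Step 3: the FAS can also shrink.** It requires cytarabine, which starts on day 4, and expansion patients are not replaced (section 4.4.2). At N = 41 the cut-off is 25 with power 0.762; at N = 43 it is 26 with power 0.785. A single fixed count is thus not enough even without pooling.

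**Step 4: how far case mix could matter (illustration only).** Suppose phase I patients respond at 65% and expansion patients at 45%. The rate for phase I is an assumption; the documents give no response rate for this subgroup. Adding Bin(6, 0.65) and Bin(42, 0.45), the chance of at least 28/48 is 0.085. With 3 such patients and 27/45 it is 0.045.

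**Step 5: responses known at the decision (illustration only).** Suppose the true rate is 45% throughout and the expansion opens only after at least 3 of 6 phase I responses. The protocol contains no such gate. The chance of passing the gate is 0.558, and of passing it and then reaching 28/48 is 0.037. The conditional error is 0.037/0.558 = 0.066. With 3 patients, a gate of at least 2 of 3 and cut-off 27/45, the conditional figure is 0.049.

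**The case against.** The strongest reply is that the test as written is valid. Section 8.2.5.1 prescribes an exact test at 5%, which sets its own cut-off at whatever N the FAS has. At 45 or 48 patients, alpha stays below 5% and power above 80%. The synopsis rule is tied to 42 patients, and nothing tells the analyst to apply 25 to a larger set. This stands. A reader might infer from the last column of the table that the trial runs at a 10% to 20% error rate; the document does not support that.

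Nor do the illustrations show a broken test. In Step 4 the mean rate in the pooled set is (6 × 0.65 + 42 × 0.45)/48 = 0.475, so the null hypothesis is false for the set being tested and 0.085 is not a type I error in the strict sense. In Step 5 the overall chance of passing the gate and rejecting (0.037) is below the ungated 0.0438. The stopping rule in section 3.2 concerns toxicity, and the results to be submitted under section 3.1 are safety and tolerability.

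A reader might also infer that two sample sizes are stated. That charge is weak. The synopsis row begins by naming the phase II part and follows a separate phase I count, so its natural reading is 42 expansion patients.

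Finally, pooling is pre-specified openly. That is a fair defence of intent, but it does not supply a rule for the pooled set.

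**Conclusion.** The point holds as a mismatch between the stated rule and the analysed set. The rule is right for 42 patients; the FAS will hold about 45 to 48 or more under the 3-or-6 assumption, and fewer if expansion patients never reach cytarabine. The required counts are then 27/45 or 28/48, not 25. Type I error is inflated (0.102 or 0.200) only on literal use of 25.

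Pooling brings a second, softer problem: patients from a narrower population, with responses that may be known when the expansion opens, count in the confirmatory test. The documents do not give the size of any bias, and it is bounded because these patients are only 3 to 6 of 45 to 48, plus any replaced ones. That phase I patients respond better is plausible from section 1.4, but not shown.

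A related wording gap: the FAS and per-protocol definitions refer to the MTD, while section 3.2 foresees that no MTD is reached and the highest level becomes the RP2D. Read literally, no patient would then qualify for either set.

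This should be fixed, but it does not invalidate the exact test.

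**What to change.** - In section 8.2.2.1, define the primary-analysis set as the expansion patients (planned 42) treated at the RP2D and exposed to both drugs. Keep 25/42, and state that the exact test governs if the actual number differs.
- Report all patients treated at the RP2D, phase I included, as a sensitivity analysis.
- If pooling is kept for the primary test, state instead that the cut-off follows the actual FAS size, and list it for each possible N (for example 27 at 45 and 28 at 48).
- In the synopsis Sample Size row, say 42 expansion patients.
- In the FAS and per-protocol definitions, replace the reference to the MTD by the RP2D.

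**Cost.** Wording only, and no extra patients on the natural reading that 42 are enrolled in the expansion. If 42 had been meant to include phase I, the change would add the 3 to 6 patients counted there. The headline estimate loses the 3 to 6 or more pooled phase I patients, so it is slightly less precise. Planned power stays at 0.818 with all 42 in the set; it would be 0.806 or 0.868 in a pooled set of 45 or 48.

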### **8.2.2.2 Per protocol set (PPS)**

Consists of all patients in the FAS who received the minimum of the planned dose of venetoclax and cytarabine (see section [3.2.1](#)) with the MTD.

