### **Concomitant Use with Other Medications**

During Phase I/Escalation part, strong and moderate CYP3A inhibitors and inducers (see [Appendix 1](#)) are prohibited.

If a patient critically needs e.g. anti-fungal treatment **after** the end of the venetoclax treatment period, that should be discussed with the coordinating investigator and the decision should be made based on the medical/clinical need.

For Phase II/Expansion part, the concomitant use of strong and moderate CYP3A inhibitors is allowed, but the dose of venetoclax should be reduced as described in section [5.5](#).

Venetoclax should be administered using caution with substrates or inhibitors of P-gp, BCRP, or substrates of OATP1B1/B3. If venetoclax is co-administered with warfarin, the international normalized ratio (INR) should be monitored closely.

Live-virus vaccines should not be given within 28 days prior to the initiation of study treatment, at any time during study treatment, or in the 30 days following last dose of study treatment.

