### 3.2.1 Target dose for DLT evaluation

To ensure the required number of evaluable subjects per cohort, patients have to have received at minimum the following of study treatment. This will be defined as  $\geq 3800$  mg venetoclax,  $\geq 2$  days of mitoxantrone, and  $\geq 6$  days of cytarabine in cohort 1 and  $\geq 3800$  mg venetoclax  $\geq 2$  days of mitoxantrone, and  $\geq 2.5$  days of cytarabine in cohorts 2+3. The dosage of mitoxantrone and cytarabine has to be according to protocol.

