#### **4.4.2 Replacement**

Subjects who experience a DLT will NOT be replaced.

In the dose escalation part of the trial (i.e. phase I), following patients should be replaced to ensure the required number of evaluable subjects per cohort:

- subjects not experiencing a DLT who have taken less than the required study treatment as described in section [3.2.1](#)
- subjects with incomplete DLT evaluation period due to any reason other than a DLT even if they have received the required study treatment (section [3.2.1](#))

In the expansion part of the trial (i.e. phase II), subjects will not be replaced.

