### Venetoclax

**Day 1 of venetoclax will define the study treatment start.** To mitigate the potential risk of TLS, venetoclax administration will start with a pre-specified dose ramp-up to reach the target dose level of 400 mg at day 4 (refer to Table 2).

Table 2: Venetoclax ramp up

Day	Venetoclax dose
1	50 mg
2	100 mg
3	200 mg
4 – 14 (10)*	400 mg

\* Venetoclax will be administered until day 14, only at dose level -1, venetoclax will be given until day 10.

Each dose of venetoclax should be taken with approximately 240 ml of water within 30 minutes after the completion of a meal, preferably breakfast. The dose should be administered at the same time each day. On days with planned cytarabine administration, venetoclax must be given prior to cytarabine and mitoxantrone. If a patient develops any lab changes suggestive of TLS within the first 24 hours after either first dose or during ramp up, venetoclax should be withheld until normalization of lab changes. Venetoclax will be administered in Phase I and II no longer than 10/14 days except during maintenance therapy.

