#### Expansion Phase:

For the phase 2 part of the protocol, the below dose modification according to the following [Table 8](#) is recommended in case of co-administration with strong / moderate CYP3A inhibitors.

Table 8: Venetoclax in case of strong and moderate CYP3A inhibitors

Inhibitors	Initiation and Ramp-Up	Venetoclax Daily Dose (after Ramp-Up)
Strong CYP3A inhibitor	Day 1 – 10 mg Day 2 – 20 mg Day 3 – 50 mg Day 4 – 100 mg or less	100 mg or less
Moderate CYP3A inhibitor (reduce the Venetoclax dose by at least 50%)	Day 1 – 20 mg Day 2 – 50 mg Day 3 – 100 mg Day 4 – 200 mg	200 mg

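### The phase II per-protocol set uses a fixed 3800 mg venetoclax minimum that patients following the CYP3A-inhibitor dose reduction miss unless the inhibitor starts late; dose level -1 has no stated minimum

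*Protocol*

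**What the plan says.** **The minimum.** Section 3.2.1 introduces it for dose escalation: "To ensure the required number of evaluable subjects per cohort, patients have to have received at minimum the following of study treatment". For the first cohort it reads: "This will be defined as $\geq 3800$ mg venetoclax, $\geq 2$ days of mitoxantrone, and $\geq 6$ days of cytarabine in cohort 1". The same 3800 mg is repeated with a shorter cytarabine requirement, in "days of cytarabine in cohorts 2+3". Dose level -1 is not named.

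**Where it is used.** The phase II PPS in section 8.2.2.2 reads "Consists of all patients in the FAS who received the minimum of the planned dose of venetoclax and cytarabine" and cites section 3.2.1. In phase I, section 8.1.2.1 builds the MTD analysis set from patients with a DLT plus those who reached the minimum for their cohort. Section 4.4.2 replaces "subjects not experiencing a DLT who have taken less than the required study treatment as described in section" 3.2.1.

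**The schedules.** Table 2 (section 5.4.1) gives venetoclax 50, 100 and 200 mg on days 1 to 3, then 400 mg to day 14, except that "only at dose level -1, venetoclax will be given until day 10". In phase II other totals arise by design. Section 1.3.2 states: "For Phase II/Expansion part, the concomitant use of strong and moderate CYP3A inhibitors is allowed, but the dose of venetoclax should be reduced". Section 5.4.2 makes the modification mandatory, and Table 8 in section 5.5 sets it out:
- strong inhibitor: 10, 20 and 50 mg on days 1 to 3, then no more than 100 mg daily;
- moderate inhibitor: 20, 50 and 100 mg on days 1 to 3, then 200 mg daily.

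**Role of the PPS.** Section 8.2.5 places all efficacy analyses in the FAS and makes the PPS a sensitivity analysis.

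**The concern.** A per-protocol set should separate patients who took the treatment the protocol assigned to them from those who did not. Here the criterion is a milligram total that fits one schedule, while the protocol assigns several. A patient who takes every tablet Table 8 prescribes can be classed as not treated per protocol.

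The exclusion is also selective. It removes patients given azoles or other CYP3A inhibitors, who may differ clinically from the rest. The FAS includes phase I patients treated at the MTD (section 8.2.2.1), for whom these inhibitors were prohibited (section 1.3.2 and Table 7). The PPS is therefore tilted towards phase I patients and inhibitor-free phase II patients. If the CR/CRi rate differed between FAS and PPS, the difference could not be read as an effect of adherence.

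The level -1 gap has a different consequence. Level -1 is the fallback if level 1 shows two or more DLTs (section 3.2). Replacement and membership of the MTD set would then depend on a threshold that has not been written.

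**Working it through.** **Step 1. Reproduce 3800 mg.** Standard 14-day course (Table 2): 50 + 100 + 200 + 11 × 400 = 4750 mg. 3800 / 4750 = 0.80. The figure is exactly 80% of the standard course, although the protocol does not express it as a percentage.

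**Step 2. Totals under full adherence to each other schedule.**

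| Schedule | Sum | Total (mg) | Share of 3800 mg |
|---|---|---|---|
| Strong inhibitor, days 1-14 | 10 + 20 + 50 + 11 × 100 | at most 1180 | 31% |
| Moderate inhibitor, days 1-14 | 20 + 50 + 100 + 11 × 200 | 2370 | 62% |
| Level -1, days 1-10, no inhibitor | 50 + 100 + 200 + 7 × 400 | 3150 | 83% |

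**Step 3. Inhibitor started later.** Assume the standard ramp-up, 400 mg daily from day 4 until the day before the inhibitor starts (day s), and the reduced dose d from day s to day 14. The total is 350 + 400 × (s − 4) + d × (15 − s), with d = 200 (moderate) or at most 100 (strong).

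| Start day s | Moderate (mg) | Strong (mg, at most) |
|---|---|---|
| 5 | 2750 | 1750 |
| 10 | 3750 | 3250 |
| 11 | **3950** | 3550 |
| 12 | 4150 | **3850** |

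The minimum is first reached at day 11 (moderate) and day 12 (strong, at 100 mg daily). The slack explains this: 4750 − 3800 = 950 mg. Each moderate-inhibitor day costs 200 mg, so four days fit (800 mg) and five do not (1000 mg). Each strong-inhibitor day costs at least 300 mg, so three days fit (900 mg) and four do not (1200 mg).

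**Step 4. Level -1.** Section 3.2.1 gives minima for cohorts 1, 2 and 3. Section 5.4.1 speaks of cohort -1 when describing mitoxantrone, so cohort numbers follow dose levels and level -1 is simply absent. If 3800 mg were carried over, full adherence would fall short by 3800 − 3150 = 650 mg.

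**Step 5. Is the primary test touched?** The design in section 8.2.1 and the Synopsis (null rate 45%, alternative 65%, 42 patients, rejection at 25 responders) gives an exact one-sided error of 0.0415 and power of 0.818. 42 is the smallest sample size meeting 5% and 80%. None of this uses the PPS or the 3800 mg figure.

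**Step 6. A proportional rule, for illustration.** Taking 80% of each planned total gives 3800 mg (standard), 0.8 × 3150 = 2520 mg (level -1), 0.8 × 2370 = 1896 mg (moderate throughout) and 0.8 × 1180 = 944 mg at most (strong throughout). These are analysis-set thresholds, not dosing proposals.

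**The case against.** - **Only a sensitivity analysis is involved.** This stands. The FAS is defined by exposure without a dose minimum, and the confirmatory test is run there. A reader might infer that the phase II decision is compromised; it is not.
- **Some inhibitor patients do qualify.** This stands. A reader might infer that no patient on an inhibitor can enter the PPS. Step 3 shows that late starters can.
- **Early inhibitor use may be uncommon.** Section 4.2 excludes strong and moderate inhibitors during screening, section 1.3.2 (Contraindications) rules them out at initiation and titration, and the note to Table 7 recommends other antifungals for suspected infection on venetoclax days. This bears on frequency but does not remove the problem. Table 8 provides an inhibitor ramp-up from day 1, section 5.1.2 supplies 10 mg tablets for the purpose, and a start on day 5, after ramp-up, still falls short.
- **The number excluded cannot be stated.** This stands. An assumed share of 20% to 80% on an inhibitor throughout would give 42 × 0.20 = 8.4 to 42 × 0.80 = 33.6 patients, but that range only restates the assumption. It is not a lower bound, and it ignores the phase I patients in the FAS.
- **The PPS wording may mean each patient's own plan.** That may be the intention, but the only definition it cites is the absolute figure.
- **Level -1 has no threshold rather than an impossible one.** This stands. A reader might infer an arithmetic contradiction in which every DLT-free patient at that level must be replaced. That follows only if 3800 mg is carried over, which the protocol does not do.
- **This could be left to the SAP.** The protocol did not leave it open; it fixed the number by cross-reference.

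**Conclusion.** The point holds as a correction to an analysis set. Section 8.2.2.2, read with section 3.2.1, excludes compliant phase II patients from the PPS if they take a moderate inhibitor from day 10 or earlier, or a strong one from day 11 or earlier. Under full adherence with the inhibitor throughout, they reach at most 62% (moderate) or 31% (strong) of the required total. These cut-off days assume a 14-day course, no missed doses, and an inhibitor that continues to day 14 once started.

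The consequence is that the FAS-versus-PPS comparison mixes adherence with inhibitor use. Among patients on the standard schedule the threshold still measures adherence, so the PPS is distorted rather than meaningless. The number affected is unknown. The primary FAS test, sample size and rejection boundary are unaffected.

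Level -1 is a separate, conditional gap. It matters only if that level opens, but then sections 4.4.2 and 8.1.2.1 call on a minimum that section 3.2.1 does not give.

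**What to change.** 1. In sections 3.2.1 and 8.2.2.2, define the venetoclax minimum as a proportion of the cumulative dose the protocol specifies for that patient's dose level and co-medication. A proportion of 80% reproduces the sponsor's own 3800 mg on the standard course.
2. For strong inhibitors, where Table 8 gives a ceiling and not a fixed dose, use the dose actually prescribed as the denominator.
3. State the evaluability minimum for level -1 in section 3.2.1, for venetoclax and cytarabine, so that sections 4.4.2 and 8.1.2.1 can be applied.
4. Reconcile section 1.3.2 (Contraindications) and section 4.2 with Table 8, which has an inhibitor ramp-up from day 1. Which rule applies is for the sponsor to settle. The answer determines which planned totals can occur.

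The cost is a few sentences and one derived variable. Concomitant medication with dates and dose is already recorded in the eCRF (section 5.5), and administered dose relative to planned dose is already to be reported (sections 8.1.5.1 and 8.2.7.1). The substantial amendment foreseen in section 3.1 before expansion is a natural place for the change. No dosing changes.
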